1.3 Schema

Week 1 through Week 4	Enrollment and Training

 • Total n=5 anesthesiologists, 10 CRNAs/anesthesia residents/fellows (user subjects) • Identify user subjects - anesthesiologists and their teams of CRNAs, anesthesia residents and fellows performing planned airway procedures under general anesthesia. • Obtain informed consent from willing user subjects and complete intake questionnaire • Document and record contact information for user subjects • Review user manual and device use. 	
Week 1 through Week 6	Device Use and Assessment

 • Protective device use and aerosol evacuation during airway procedures under general anesthesia on COVID-19-negative patients • Patients (patient subjects) of anesthesiologists participating as user subjects in the study will be recruited on the day of procedure. • Patient subjects will be randomized to intubation with or without the biocontainment device. • Goal of obtaining data from 150 airway procedures under general anesthesia in the device (100 with the device and 50 without the device). • Patient subject Data and data from record of airway procedure will be recorded after each device use • Quality Use Survey, including documentation of any AEs will be completed by user subjects at the end of each day • Patient experience questionnaire completed by patient subject randomized to device use within 1 week after procedure 	

- AE event summary reconciliation and review performed weekly
- Feedback on quality use data use and user suggestions given to engineering team every two weeks
- Interval assessment by the medical director of intubation data from medical record, quality use survey data, including summary of AEs, and preliminary analysis of post-training questionnaire/intake data every two weeks

Week 4 through Week 12	Device Use and Assessment, Final Data Analysis
	
• Continued use and assessment of biocontainment device if needed to meet enrollment numbers• Final Feedback on device use and user suggestions given to engineering team• Final assessment of survey data and device utilization

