Patient Subject Experience Survey: The patient subject's randomized to device use will be asked in the recovery room post-procedure or receive a phone call or email with REDCap survey link from a qualified study coordinator to answer a short patient experience survey where the data will be collected in REDCap and subsequently transcribed into CTMS. Data collected will include: 1) overall comfort in the device, 2) sensation of increased anxiety, 3) sensation of claustrophobia, 4) perceived safety in the device, 5) any difficulties seeing or hearing while in the device, 6) any additional comments or suggestions regarding the experience in the device. All data will be collected on a Likert scale and stored in CTMS.

Patient subjects' medical records medical will be accessed as part of the study. Personal and medical data collected as part of the study will be stored in a de-identified fashion on an institutionally secured and managed network drive and/or computer.

As part of this study, user subjects' medical records will NOT be accessed. Personal data including age, and gender, will be collected as part of the initial data collection instrument and stored in de-identified fashion on an institutionally secured and managed network drive and/or computer.

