9 STATISTICAL CONSIDERATIONS

9.1 *Statistical Hypotheses*

We hypothesize that the biocontainment device will be a safe and effective option for performing airway procedures in patients while also providing additional protection during an aerosol generating procedure.

Primary Efficacy Endpoints:

1. We hypothesize that the time to perform an airway procedure with the biocontainment device will be equivalent to time for airway procedure without the biocontainment device. Alternatively, there will be prolonged airway procedures times with the device. This endpoint will be analyzed every two weeks.
2. We anticipate that the number of AEs or ADEs will be low and will also decrease over time. This endpoint will be analyzed on a weekly basis.

Secondary Efficacy Endpoints:

1. We hypothesize that the median Likert ratings for User subject device comfort will be weighted toward “strongly agree”. Alternatively, we will see ratings favoring “neutral” or “disagree” for user subject device comfort.
2. We hypothesize that the median Likert ratings for User subject additional healthcare burden comfort will be weighted toward “strongly disagree”. Alternatively, we will see ratings favoring “neutral” or “agree” on increased healthcare burden.
3. The median Likert ratings for the Patient Experience survey will be weighted toward minimal patient discomfort or anxiety. Alternatively, we will see ratings favoring increased patient discomfort or anxiety inside the device.
3. We anticipate that the median Likert ratings of the patient experience post-survey will indicate overall good user comfort and low levels of anxiety or claustrophobia in the device.

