9.4 Statistical Analyses

9.4.1 General Approach

Descriptive statistics:

- The number of subjects who utilized the protective device will be included; the level of experience and training of user subjects will be included.
- Patient subject baseline demographics, co-morbidities, smoking status, and intubation-related factors will be included.
- Objective data regarding total time for the airway procedure, number of intubation/LMA/extubation attempts, airway device used (i.e. intubation blade used and size of ETT) will be included.
- The user subjects comfort level for device use will be graded on a continuous scale, and the mean comfort level calculated as well as the range.
- The patient subjects comfort level and experience in the device will be graded on a continuous scale, and the mean comfort/experience level calculated as well as the range.
- Categories for various healthcare burdens will be provided as options for participants; the mean for most common burden will be identified; the percentage for each burden subtype will also be identified.

Inferential Tests

- A p-value of 0.05 and 95% confidence interval will be utilized when determining if the protective device results in an improvement in outcomes measures, i.e. a decrease in the number of COVID-19 cases by participants.
- Chi-square testing or ANOVA will be used.

Covariates will be collected on participants, including but not limited to subspecialty training, years of experience as a resident, fellow, or attending, as well as gender.

Assumption of normality of data points will be determined using Q-Q plots. If there are limitations to performing assumptions of normality, then appropriate non-parametric corrections would be performed.

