9.4.3 Analysis of the Secondary Endpoint(s)

The secondary endpoints are not dependent on the primary endpoints.

1. Device Use Survey questions that are specific to the functioning of the device are collected as ordinal data on a Likert scale. Data will be presented as the median value with standard deviation for individual question results. Aggregate (summed) results for all questions will be also be assessed using the same methodology. Statistical significance will be determined using Chi-square test. Sub-analysis will be performed based on user subject experience level.
2. Device Use Survey questions that are specific to the healthcare burden associated with the device are collected as ordinal data on a Likert scale. Data will be presented as the median value with standard deviation for individual question results. Aggregate (summed) results for all questions will be also be assessed using the same methodology. Statistical significance will be determined using Chi-square test. Sub-analysis will be performed based on user subject experience level.
3. Patient experience survey results are collected as ordinal data on a Likert scale. Data will be presented as the median value with standard deviation for individual question results. Aggregate (summed) results for all questions will be also be assessed using the same methodology. Statistical significance will be determined using Chi-square test. Sub-analysis will be performed based on patient age, gender, co-morbid conditions, type of airway procedure performed.

Statistical analyses will be performed on all data points, however, a sub-analysis will be performed on participants without any missing data points.

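### The chi-square test for the device-arm patient ratings has no stated null or direction, so p<0.05 would not by itself support the hypothesis that ratings lean favourable

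*Combined protocol and SAP*

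**What the plan says.** Section 9.1 sets a directional hypothesis for the patient survey: "The median Likert ratings for the Patient Experience survey will be weighted toward minimal patient discomfort or anxiety". Its alternative points the other way: "Alternatively, we will see ratings favoring increased patient discomfort or anxiety inside the device".

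The survey is given in one arm only. The schema in section 1.3 reads "Patient experience questionnaire completed by patient subject randomized to device use within 1 week after procedure", and section 8.1 agrees: "The patient subject's randomized to device use will be asked in the recovery room post-procedure". The planned split is "100 with the device and 50 without the device", so at most about 100 surveys are expected and none from controls.

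Section 9.4.3 item 3 describes the data and the test: "Patient experience survey results are collected as ordinal data on a Likert scale". Each question, and the sum over questions, is to be summarised by a median with standard deviation. Then: "Statistical significance will be determined using Chi-square test. Sub-analysis will be performed based on patient age, gender, co-morbid conditions, type of airway procedure performed". Items 1 and 2, on the user surveys, name the same test.

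Section 9.4.1 sets the threshold: "A p-value of 0.05 and 95% confidence interval will be utilized when determining if the protective device results in an improvement in outcomes measures". Neither section gives null proportions, a reference category, a grouping of categories or a direction for the chi-square.

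**The concern.** The hypothesis concerns location and direction on an ordered scale in a single group. A Pearson chi-square on category counts uses neither order nor direction. With no control surveys there is no between-arm table to test, which leaves two natural readings. One is goodness of fit against equal use of all categories. The other is association between rating and the subgroups named in the next sentence. Neither has the null that 9.1 implies.

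What is at stake is how a secondary endpoint is interpreted. A p-value below 0.05 printed beside a median could be taken as evidence that patients were comfortable, when it shows only that the categories were not used equally or that subgroups differed.

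**Working it through.** **The plan's own figure.** The documents give no power or error figure for this test. The only sample-size figure, 97 procedures in section 9.2, is a single-proportion precision calculation: 1.96² × 0.25 / 0.1² = 3.8416 × 0.25 / 0.01 = 96.04, rounded up to 97. It says nothing about the Likert ratings.

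**Inputs from the documents.** Alpha 0.05 (9.4.1); 100 device patients (1.3); device-arm survey only (1.3, 8.1); ordinal Likert data (9.4.3).

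**Assumptions.** Five levels, ordered from worst to best; an equal-proportions null; independent responses; the rating shapes below; and 85 returned surveys as a lower case, from 100 × (1 − 0.15). Section 9.2 gives 10-15% as a drop-out or screen-failure rate, and applying it to survey return is my assumption.

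**Step 1: direction.** With n=100 and an expected count of 20 per level:

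- Favourable counts 5/10/15/30/40: (225 + 100 + 25 + 100 + 400)/20 = 42.5, p = 1.3 × 10⁻⁸.
- Unfavourable counts 40/30/15/10/5: the same five terms in reverse order, again 42.5 and the same p.

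This holds for any set of counts and its mirror image, so it does not depend on the shapes chosen.

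**Step 2: chance of p<0.05 under the equal-proportions reading.** The noncentrality is n × Σ(pᵢ − 0.2)²/0.2, with 4 df and critical value 9.49. For 10/20/40/20/10 the sum is (0.01 + 0 + 0.04 + 0 + 0.01)/0.2 = 0.30, which gives 30 at n=100 and a rejection probability of 0.997. In the same way:

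| True ratings, worst to best (%) | Sum | n=100 | n=85 |
|---|---|---|---|
| Neutral peak 10/20/40/20/10 | 0.300 | 0.997 | 0.991 |
| Sharper neutral peak 5/20/50/20/5 | 0.675 | >0.999 | >0.999 |
| Unfavourable 30/30/20/15/5 | 0.225 | 0.980 | 0.956 |
| Strongly unfavourable 40/30/15/10/5 | 0.425 | >0.999 | >0.999 |
| Unfavourable, less skewed 25/30/20/15/10 | 0.125 | 0.82 | 0.75 |
| Flatter neutral 15/20/30/20/15 | 0.075 | 0.57 | 0.50 |
| Mildly unfavourable 26/23/20/17/14 | 0.045 | 0.36 | 0.31 |
| Uniform | 0 | 0.05 | 0.05 |

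If the other four levels are equal, 95% rejection needs a neutral share of about 37.5% (n=100) or 39% (n=85).

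**Step 3: subgroup reading.** A 2×5 chi-square with no true subgroup difference rejects about 4.5% of the time, both for the neutral-peak and for the strongly unfavourable ratings. It is a valid test of whether subgroups differ, but it carries no information on whether ratings lean favourable.

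**Step 4: a directional test.** A one-sided signed-rank test against the middle category at n=100 (simulated) rejects about 5% of the time for the symmetric shapes. For the unfavourable shapes it rejects 0.000 to three decimals. For the favourable mirrors of 30/30/20/15/5 and 40/30/15/10/5 it rejects 1.000. The one-sided exact sign test gives about 0.04, 0.000 and 0.999-1.000.

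**Step 5: power when ratings lean mildly favourable.** For 12/15/21/25/27 at n=100 the noncentrality is 100 × 0.082 = 8.2, so the 4-df chi-square has power 0.62. The exact two-sided sign test has 0.78, a gap of about 16 points on equal sidedness.

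**The case against.** The equal-proportions null is not in the documents. A goodness-of-fit test can use any stated proportions, and a third reading exists: a 1-df chi-square of favourable against unfavourable counts. That is the large-sample two-sided form of the sign test. At n=100 it rejects about 5% of the time for symmetric neutral ratings and has power 0.82 for 12/15/21/25/27. This stands: such a test would largely address 9.1. But the plan does not specify that grouping. Being two-sided, the test also rejects 0.997 of the time for unfavourable 30/30/20/15/5, so the direction would still have to be read separately.

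The endpoint is the median, and 9.4.3 reports it. A plainly unfavourable median would show its direction, so a reader should not infer that bad ratings would be presented as comfort. This also stands. The exposure is greatest where the median is at or near the middle and the p-value appears to add support.

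A reader might infer that p<0.05 is near certain whenever ratings are neutral or unfavourable. The documents do not support that. They give no null, number of levels or expected shape, and the flatter shapes give 0.31 to 0.57, uniform ratings 0.05, and the subgroup reading about 0.05.

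Section 9.4.1 allows non-parametric corrections, but only where normality is doubtful, and it names no test. It does not replace the chi-square in 9.4.3. Finally, this is a feasibility study and no decision rule rests on these p-values. That limits the weight of the point, though the plan does attach hypotheses and significance tests to these endpoints.

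**Conclusion.** The point holds as a mismatch between a directional hypothesis and a test with no stated null or direction. A significant chi-square would not by itself support 9.1 under either natural reading. The mirror-image result needs only the equal-proportions reading. The rejection probabilities (about 0.96 to above 0.99 for clearly peaked or skewed ratings, lower for flatter ones) also rest on five levels, 85 to 100 independent surveys and the assumed shapes, so they illustrate what can happen and do not predict this trial's result.

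The same wording affects the user comfort and burden endpoints, but a reader should not infer that the patient-survey remedy carries over unchanged. Users complete a survey after each day of use (8.1) and only 15 to 20 are recruited (5.5), so a sign or signed-rank test that treats those ratings as independent would be invalid. The middle category also needs care: 9.1 names a neutral rating for the user items but not for the patient survey. This should be corrected before analysis, but it does not threaten the primary endpoints.

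**What to change.** In 9.4.3 item 3, for each patient question:

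- define which direction is favourable and which category is the reference midpoint;
- report the full response distribution and the median;
- replace the chi-square with an exact sign or Wilcoxon signed-rank test against the reference in the 9.1 direction, or with the proportion favourable and its 95% CI;
- claim a favourable result only if the reference is excluded.

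For the ordinal sub-analyses, use rank-based or proportional-odds methods. In one assumed 50 versus 50 shift (5/10/20/30/35 against 12/18/25/25/20), chi-square power was 39% and rank-sum power 62%.

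For items 1 and 2, state the same kind of directional hypothesis and use a method that allows for repeated surveys within user, such as one summary value per user, or a mixed or GEE ordinal model.

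The cost is analysis-plan wording, plus somewhat more modelling for the user surveys. No new patients, data or procedures are needed. The small downside is that a favourable claim becomes harder to make when ratings are neutral.

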9.4.4 Safety Analyses

Safety analyses is one of the primary endpoints and will be assessed as described in [Section 9.4.2](#). Reporting of AEs, SAE, ADEs, UADEs is as described in [Section 8.2](#).

9.4.5 Planned Interim Analyses

An interim analysis will be performed after 50% enrollment (approximately 4 weeks) on primary and secondary outcomes. If the total number of AEs or ADEs is trending upward over time, the study would be paused until further assessment of AE/ADEs by the study Sponsor or their qualified designee would be performed as described in [Section 8](#).

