1 STUDY SUMMARY

1.1 Synopsis

Title: Aerosol Biocontainment Device (ABCD) with Aerosol Clearance for Aerosol Generating Procedures

Short Title: Aerosol BioContainment Device (ABCD)

Study Description: The primary goal of this study is to assess use of a biocontainment device for planned airway procedures under general anesthesia. This will serve as a platform for using this device as a novel biocontainment and aerosol evacuation system as part of rapid sequence intubation protocols for COVID-19 patients. We hypothesize that airway procedures with the aerosol biocontainment device will be safe and effective with airway procedure times approaching times for airway procedures without the device.

Objectives: The primary objectives of this study are: 1) Assess changes in airway procedure time with and without the biocontainment device as a function of repeated utilization and as a function of patient-associated airway factors (i.e. Mallampati score, hyomental distance, neck mobility, BMI) and user-associated airway factors (i.e. experience of user, airway device used, induction sequence) 2) Assess adverse events, adverse device events associated with biocontainment device use.

Secondary objectives include: 1) Assess the subject's comfort with using the biocontainment device. 2) Assess for additional healthcare and cognitive burden imposed by the device. 3) Survey of patient's post-procedure on experience being inside the device. Exploratory objectives include gathering specific feedback regarding possible design modifications for further iterations and design improvements with the engineering team.

Primary Endpoint: The primary endpoints of this study are:
1. Measuring the time for performing an airway procedure with the biocontainment device when accounting for patient and user-specific factors.
2. Quantifying the number of AEs or ADEs over time to assess device safety.

Secondary Endpoints: The secondary endpoints include:
1. Median Likert ratings from device use survey questions that assess user subject device comfort.
2. Median Likert ratings from device use survey questions that assess user subject healthcare burden with the device.
3. Median Likert rating of the patient questionnaire results to assess patient experience in the device.

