3 STUDY OBJECTIVES AND ENDPOINTS

The objectives of this study are to evaluate efficacy of training and use by frontline healthcare workers of a biocontainment system that provides additional protection during aerosol-generating procedures with COVID-19 patients. The primary objectives of this study are: 1) Assess changes in airway procedure times with and without the biocontainment device as a function of repeated utilization and as a function of patient-associated airway factors (Mallampati score, hyomental distance, neck mobility, BMI) and user-associated airway factors (experience of user, airway device used, induction sequence) and 2) Assess adverse events, adverse device events associated with biocontainment device use. Secondary objectives include: 1) Assess the subject's comfort with using the biocontainment device, 2) Assess for additional healthcare and cognitive burden imposed by the device. 3) Survey of patient's post-procedure on experience being inside the device. Exploratory objective includes gathering specific feedback regarding possible design modifications for further iterations and design improvements with the engineering team.

OBJECTIVES	ENDPOINTS	JUSTIFICATION FOR ENDPOINTS
Primary		

 1. Assess changes in airway procedure times with and without the biocontainment device as a function of repeated utilization and as a function of patient-associated airway factors (Mallampati score, hyomental distance, neck mobility, BMI) and user-associated airway factors (experience of user, airway device used, induction sequence). 2. Assess adverse events, adverse device events associated with using the biocontainment device. 	
 1. Measuring the time for performing an airway procedure with the biocontainment device when accounting for patient and user-specific factors. Sub-analysis, based on user experience level. 2. Quantifying the number of AEs or ADEs over time to assess device safety. Breakdown of AEs/ADEs as a function of time and by user subject. 	These endpoints were chosen to assess the safety and efficacy of biocontainment device use over time. This will help assess the viability of the device as an additional layer of protection for aerosol-generating procedures.
Secondary		

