8.3.2 Classification of an Adverse Event

8.3.2.1 Severity of Event

Adverse events will be classified based on the defined grading system:

- Mild: events require minimal or no treatment and do not interfere with the participant's daily activities
- Moderate: events result in low level of inconvenience or cause some inference with functioning
- Severe: events interrupt a participant's usual daily activity. Severe events are usually potentially life-threatening or incapacitating. Please note, the term "severe" does not necessarily equate to "serious".

8.3.2.2 *Relationship to Study Intervention*

All adverse events (AEs) and ADEs must have their relationship to the study device assessed by the PI who examines and evaluates the participant based on temporal relationship and his/her clinical judgment. The degree of certainty about causality will be graded using the categories below. In a clinical trial, the study product must always be considered.

- Definitely Related – The AE/ADE is known to occur with the device.
- Probably Related – There is a reasonable possibility that the device caused the AE, or there is a temporal relationship between the device use and event. Reasonable possibility means that there is evidence to suggest a causal relationship between the device and the AE/ADE.
- Possibly Related - There is a possibility that the device caused the AE, or there is a temporal relationship between the device use and event. There is no evidence to suggest a causal relationship between the device and the AE/ADE but an alternate etiology has not yet been established.
- Unrelated – There is not a reasonable possibility that the use of the device caused the event, there is no temporal relationship between the use of the device and event onset, or an alternate etiology has been established.

8.3.2.3 *Expectedness*

Expected adverse events associated with this study that will be tracked and reported include:

1. Minor injury to the patient subject or provider
2. Patient claustrophobia
3. Patient anxiety
4. Difficulty performing intubation with the device in place
5. Need to remove the biocontainment device to safely perform intubation

Potential SAEs associated with this study would include:

1. Major physical injury to patient or provider due to device failure.

A UADE for this device would be breakdown or malfunction of the device during use.

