8.3.3 Time Period and Frequency for Event Assessment and Follow-Up

Safety will be assessed by monitoring and recording potential adverse effects using the quality use survey and the patient survey questionnaire as defined in [Section 1.3](#). Participants will be monitored by these questionnaires. Any adverse events/ADEs are captured and shared with study PIs and the Sponsor. AEs and SAEs will be assessed for daily and completeness of surveys (data integrity) will be assessed weekly.

The investigator will seek information on adverse events by non-directive questioning. Adverse events may also be detected when they are volunteered by the clinician utilizing the device. Information on all adverse events will be recorded in the source documentation. To the extent possible, adverse events will be recorded as a diagnosis and symptoms used to make the diagnosis recorded within the diagnosis event.

As much as possible, each adverse event or follow-up information will be evaluated to determine:

1. Severity grade (as described in [Section 8.3.2.1](#) above)
2. Duration (start and end dates)
3. Relationship to the study treatment or process – (As described in [Section 8.3.2.2](#) above)
4. Expectedness to study treatment or process – [Unexpected – if the event severity and/or frequency is not described in the investigator brochure (if applicable) or protocol].
5. Action taken with respect to investigational device or process (none, permanently discontinued, unknown, not applicable)
6. Whether the event is serious

Once an adverse event is detected, it should be followed until its resolution or until it is judged to be permanent, and assessment should be made weekly (or more frequently, if necessary) of any changes in severity, the suspected relationship to the study treatment, the interventions required to treat it, and the outcome.

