9.4.2 Analysis of the Primary Efficacy Endpoint(s)

Primary Endpoints:

1. Assessment of time to complete an airway procedure with or without the biocontainment device. The time is measured as a single quantitative measure at the end of the procedure. The initial starting time (T0) is defined as “time the mask is removed from the patient just prior to initiation of the airway procedure”. End time (T1) is defined as the time that the airway procedure is completed with a secure airway defined as the

time the airway device is secured to the airway circuit. Data will be presented as median amount of time for a given procedure with or without the biocontainment device and statistical significance will be determined by analysis of variance (ANOVA). Additionally, a multiple regression model will be created using covariates of subject user experience, number of prior uses with the device, and patient specific factors (co-morbid conditions, BMI, Mallampati score). This will help determine the critical factors associated with time to use the device.

2. The total number of AEs and ADEs will be presented. This will be broken down by specific AE or ADE. Logistic regression will be used to assess possible contributing factors to AEs or ADEs including subject user experience, airway procedure performed, patient-specific factors (BMI, co-morbid conditions, Mallampati score). We anticipate a low number of AEs/ADEs and as such, statistically rigorous regression analyses may be limited by a low overall number of events.

Statistical analyses will be performed on all data points, however, a sub-analysis will be performed on participants without any missing data points.

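### The interim AE trend (9.4.5) and the primary safety analysis (9.4.2, 9.4.4) make no use of the recorded severity grade or seriousness, and sections 8.2, 9.4.5 and 10.1.2 set different conditions for pausing

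*Combined protocol and SAP*

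**What the plan says.** Safety is one of the two primary endpoints. The synopsis (1.1) defines it as "Quantifying the number of AEs or ADEs over time to assess device safety", and the objectives table in section 3 adds "Breakdown of AEs/ADEs as a function of time and by user subject". Section 9.4.4 adds no analysis of its own: "Safety analyses is one of the primary endpoints and will be assessed as described in" section 9.4.2. There, item 2 reads "The total number of AEs and ADEs will be presented. This will be broken down by specific AE or ADE", followed by a logistic regression on possible contributing factors.

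On the interim look, 9.4.5 says "An interim analysis will be performed after 50% enrollment (approximately 4 weeks) on primary and secondary outcomes", and then "If the total number of AEs or ADEs is trending upward over time, the study would be paused" until the sponsor or a designee has assessed the events.

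Severity information is foreseen. Section 8.3.2.1 says "Adverse events will be classified based on the defined grading system" and defines mild, moderate and severe. Section 8.3.3 lists the severity grade as the first item to be determined for each event, and "Whether the event is serious" as the last, with the proviso that this is done as far as possible. No analysis in section 9 uses either item.

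**The concern.** A count in which every event weighs the same follows whichever kind of event is most common. Of the five expected events in 8.3.2.3, several (minor injury, anxiety, claustrophobia) are likely to be mild in most cases. Section 9.1 predicts that the overall number will be low and will fall over time. A falling total is thus the planned-for result and would read as reassurance, even if the events that remained were becoming more serious. Conversely, a run of mild events could trigger a pause with no change in serious harm.

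At stake is how informative the one trend-based trigger in the statistical section is, and how well the final report can describe the severity of events for a device that, per the synopsis, has not been used before in a healthcare setting.

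**Working it through.** **No figure to reproduce.** Section 9.4.5 gives no threshold, error rate, denominator or definition of an upward trend. The documents give no event rates. All rates below are assumptions, shown as a range.

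**Inputs from the documents.** The schema (1.3) plans 150 procedures, 100 with the device and 50 without; 6.3 gives 2:1 randomization. Half of enrolment is 75 patients, and 75 × 2/3 = 50 device uses. I split these into two consecutive halves of 25.

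**Assumed reading of the trigger.** The trend is upward if the count in the second 25 uses (Y) exceeds that in the first 25 (X): P(Y > X) = Σₓ P(X = x) · P(Y > x).

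**Set A: Poisson counts, mean = 25 × rate.** Severe events rise from 1% to 6% per use, so expected counts go from 0.25 to 1.5.

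**Set B: binomial counts, n = 25, mild and severe independent.** Severe events rise from 2% to 8%, so expected counts go from 0.5 to 2.0.

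| Set | Mild rate, first → second half | Expected total, first → second half | P(total rises) | P(severe count rises) |
|---|---|---|---|---|
| A | 20% → 8% | 5.25 → 3.5 | 0.22 | 0.70 |
| A | 5% → 2% | 1.5 → 2.0 | 0.49 | 0.70 |
| B | 40% → 20% | 10.5 → 7.0 | 0.13 | 0.74 |
| B | 30% → 15% | 8.0 → 5.75 | 0.20 | 0.74 |
| B | 20% → 10% | 5.5 → 4.5 | 0.30 | 0.74 |
| B | 10% → 5% | 3.0 → 3.25 | 0.46 | 0.74 |

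Example, first row: 25 × (0.20 + 0.01) = 5.25 and 25 × (0.08 + 0.06) = 3.5. The expected total falls by a third while expected severe events rise sixfold. Where mild events are rarer (second and last rows), the expected total no longer falls and most of the masking goes, although the total still rises less often than the severe count.

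**Chance rises with no change in rates.** With a constant total rate of 10% to 30% per use (Poisson means 2.5 to 7.5 per half), the total rises with probability 0.41 to 0.45. A severe-only count is not immune: with 0.875 expected severe events in each half, it rises with probability 0.33.

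**The conditions side by side.**
- 8.2: the trial goes on only if there has been no clinically significant adverse event and no unanticipated device failure. No trend is needed. Clinical significance is not defined for this clause or linked to the grades in 8.3.2.1.
- 9.4.5: a pause follows an upward trend in the total. A single event, however grave, does not meet this condition by itself.
- 10.1.2: a serious event linked to device function, or significant or unacceptable risk, is among the circumstances that may justify suspension or termination. This is discretionary.

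Taken literally, 8.2 would end the trial at an event that 9.4.5 would only count.

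**The case against.** The strongest reply is that 9.4.5 is not the only safeguard. Section 8.2 needs no trend. Section 10.1.2 allows suspension. Section 8.3.4 requires serious events and unanticipated device effects to be reported within 24 hours, 8.3.5 requires review at least weekly, and the schema adds a two-weekly assessment by the medical director. Section 8.3.2.1 describes severe events as usually potentially life-threatening or incapacitating, so few would escape the clause in 8.2. On the assumed rates, at least one severe event among 50 device uses has probability 1 − exp(−1.75) = 0.83 in set A and 1 − 0.98²⁵ × 0.92²⁵ = 0.92 in set B. This stands. A reader might infer from 9.4.5 that the study would carry on unpaused while severe events increased; the documents as a whole do not support that.

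Three further replies stand in part:
- The split by event type partly separates severity, because 8.3.2.3 lists minor injury apart from major injury, and 9.4.7 lists individual data. So the final report would not be a bare sum. But anxiety or a difficult intubation can be of any grade, and the 9.4.5 trigger uses only the total.
- Section 9.1 predicts a fall in the overall number, not in mild events specifically. The falling mild rates are my assumption. Each patient is in the device only once, so any learning would be the users'.
- Grading is done as far as possible, so some grades may be missing.

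The oversight routes do not replace a prespecified analysis of a primary endpoint by grade.

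**Conclusion.** The point holds in limited form. The 9.4.5 trend and the primary safety analysis use AE/ADE counts without severity grade or seriousness, although both are to be recorded. Read alone, the 9.4.5 trend can miss a worsening mix or respond to mild events only.

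The size is not fixed by the documents. In the scenarios examined, the total rises with probability about 0.13 to 0.49, against about 0.70 to 0.74 for severe events alone. The gap is wide when mild events are common and falling, and much narrower when they are rare. These figures rest on assumed rates, independent events and a simple comparison of two halves of 25 device uses. They describe one sentence of the plan, not its whole safety oversight.

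Separately, and without any assumed rate, 8.2, 9.4.5 and 10.1.2 give different conditions for continuing or pausing and need to be reconciled.

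**What to change.** 1. In 9.4.2 item 2 and 9.4.4, add a table of AEs/ADEs by severity grade and by seriousness, with the number of device uses as denominator and a row for events without a grade. I do not ask for a comparison by arm: the adverse event definition in 8.3.1.1 refers to device use, the patient survey goes only to the device arm, and the Quality Use Survey follows days on which the device is used, so control-arm events are not captured in the same way.
2. In 9.4.5, report the interim trend per device use for mild events and for moderate, severe or serious events, as well as in total, and say how a trend will be judged.
3. Reconcile 8.2, 9.4.5 and 10.1.2 on when the study pauses. The criterion is for the sponsor to choose; none is proposed here.

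The cost is some wording and one extra table from fields that 8.3.3 already lists. The downside is that counts in the higher-severity group will be small and their trend imprecise, as the 0.33 chance of a rise with no true change shows.
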